14 TECHNICAL DETAILS

Estimation of NCA parameters will be performed in a validated version of Phoenix WinNonlin version 8.3 or later, or a similar software package. Phoenix WinNonlin, SAS version 9.4 or later or R statistical computing software 4.3.1 or higher will be used to generate all tables, figures, and listings.

15 SUMMARY OF CHANGES IN THE CONDUCT OF THE STUDY OR PLANNED ANALYSES

No changes in the conduct of the study or planned analysis.

17 LISTING OF TABLES, FIGURES, AND LISTINGS

Table, figure, and listing shells are presented in Appendices 1, 2, and 3.

[Global Programming Note: Only columns, legends, and any other impairment group indicators in the table, figure, and listing shells that were enrolled in the study will be included in the outputs. For example, if only the Severe Renal Impairment and Matched control groups are enrolled, columns, figure legends, or other indicators for the Mil and Moderate Renal Impairment groups may be removed.

The Severe Renal Impairment arm will be displayed in two separate columns as "Severe Renal Impairment" and "ESRD, Not on Dialysis" in tables and figures.]

APPENDICES

9.1 Overall Study Design and Plan Description

Table 1: Study Design

[Implementation Note: Study design chart or schematic can be excerpted from the protocol and include here. If a schematic or flow chart is used instead of a chart, rename as Figure 1 and move to Appendix 2.]

Part A

Group	N	Participant Characteristics	Stage ^a	eGFR ^b
1A	6	Healthy matched participants (controls) with normal renal function	N/A	≥90
2	6	Severe renal impairment and ESRD not on dialysis	4 5	15-29 mL/min < 15mL/min
Total	12			

Part B

Group	N	Participant Characteristics	Stage ^a	eGFR ^b
1B	6	Matched participants with normal renal function	N/A	≥90
3	6	Mild renal impairment	2	60-89
1C	6	Matched participants with normal renal function	N/A	≥90
4	6	Moderate renal impairment	3	30-59
Total	24			

CKD=chronic kidney disease; eGFR=electronic case report form; ESRD=end stage renal disease; MDRD=Modification of Diet in Renal Disease; N/A=not applicable.

^a Stage based on Clinical Practice Guidelines for CKD (National Kidney Foundation, 2002) and Guidance for Industry Pharmacokinetics in Patients with Impaired Renal Function- Study Design, Data analysis and Impact on Dosing (DHHS, FDA, and CDER 2020 Draft Guidance).

^b eGFR: estimated glomerular filtration rate based on an MDRD equation. Different mathematical formulas have been developed to determine eGFR. The MDRD eGFR formula was developed to adjust for body surface area and ethnicity, as well as considerations such as age and sex. In many ways the MDRD is superior to the Cockcroft Gault calculation as it is more precise and reliable in predicting GFR. eGFR for this study is automatically calculated by clinical laboratories.

9.5.1 Efficacy/Immunogenicity and Safety Measurements Assessed and Flow Chart

Table 2: Schedule of Study Procedures

[Implementation Note: Include a graphic display of the frequency and timing of efficacy and safety measures including visit numbers. The schedule of procedures from the protocol may be excerpted and included here, as appropriate.]

Study Visit	00A	00B	00C	01A	01B	01C	01D	01E	01F	01G	01H	01I	01J	01K	01L	01M	01N	02 ¹	03	Early Term
Study Day	Screen -28 to -7		Admit -1	1	1	1	1	1	1	1	1	1	2	2	3	4	5	12 ± 2d	85 +7d	
PK Time Window				Up to 1 hour Pre-dose ⁸	1 hr (± 10 min)	2 hr (± 10 min)	4 hr (± 10 min)	5 hr (± 10 min)	6 hr (± 10 min)	8 hr (± 10 min)	12 hr (± 10 min)	16 hr (± 10 min)	24 hrs (± 1hr)	36 hrs (± 1hr)	48 hrs (± 1hr)	72 hrs (± 4hrs)	96 hr (± 4hrs)			
Obtain Written Informed Consent	X																			
Verify Eligibility	X		X	X																
Reconfirm participant's willingness to participate		X	X																	
Medical History	X		X	X													X	X	X	X
Concomitant Medications	X		X ²	X ²	X ²	X ²	X ²	X ²	X ²	X ²	X ²	X ²	X ²	X ²	X	X	X	X	X	
12-Lead ECG	X																	X		
Vital Signs (Oral Temp, Sitting Pulse and BP) ³	X			X							X		X		X	X	X	X		X
Physical Examination	X																			
Targeted PE if needed				X	X	X	X	X	X	X	X	X	X	X	X	X	X	X	X	
Height and Weight	X																			
Urine Pregnancy Test ⁴		X	X	X													X		X	

Table 2: Schedule of Study Procedures (continued)

Study Visit	00A	00B	00C	01A	01B	01C	01D	01E	01F	01G	01H	01I	01J	01K	01L	01M	01N	02 ¹	03	Early Term
Study Day	Screen -28 to -7		Admit -1	1	1	1	1	1	1	1	1	1	2	2	3	4	5	12 ± 2d	85 +7d	
Placement of Peripheral Catheter (if applicable)			X ⁵	X ⁵																
HIV, HBsAg, HCV	X																			
Safety and Basic Lab Testing ⁶	X																X	X	X	
PK Time Window						Up to 1 hour Pre-dose ⁸	1 hr (± 10 min)	2 hr (± 10 min)	4 hr (± 10 min)	5 hr (± 10 min)	6 hr (± 10 min)	8 hr (± 10 min)	12 hr (± 10 min)	16 hr (± 10 min)	24 hrs (± 1hr)	36 hrs (± 1hr)	48 hrs (± 1hr)	72 hrs (± 4hrs)	96 hr (± 4hrs)	
Urine Drug Screen and Alcohol screening		X	X																	
In-house Confinement			X	X	X	X	X	X	X	X	X	X	X	X	X	X				
Study Product Administration ⁷					X															
Blood for PK					X ⁸	X	X	X	X	X	X	X	X	X	X	X	X	X		
Urine collection for PK and volume measurement ⁹					X	X	X	X	X	X	X	X	X	X	X	X	X	X		
Discharge from Hospital ¹²																	X			
Remove Intravenous Catheter (if applicable)																X				
Targeted Review of Systems for Renal Participants																			X	
AE/SAE Assessment				X	X	X	X	X	X	X	X	X	X	X	X	X	X	X ¹⁰	X	

Table 2: Schedule of Study Procedures (continued)

Study Visit	00A	00B	00C	01A	01B	01C	01D	01E	01F	01G	01H	01I	01J	01K	01L	01M	01N	02 ¹	03	Early Term
Study Day	Screen -28 to -7		Admit -1	1	1	1	1	1	1	1	1	1	2	2	3	4	5	12 ± 2d	85 +7d	
Pregnancy Assessment																			X	
Phone Call																			X	

AE=adverse event; ALT=alanine aminotransferase; AST=aspartate aminotransferase; BUN=blood urea nitrogen; ECG=electrocardiogram; eGFR=estimated glomerular filtration rate; HBsAg=hepatitis B surface antigen; HCV=hepatitis C virus; HIV=human immunodeficiency virus; PE=physical examination; PK=pharmacokinetic; SAE=serious adverse event

¹ Study visits 01M-02 may be outpatient at the site.

² Concomitant medications will be recorded during the entire hospital stay.

³ Participants must not eat or drink anything hot or cold within 10 minutes prior to taking oral temperature.

⁴ Must be performed on all female participants of childbearing potential prior to receipt of each study product and results must be negative and known prior to receipt of study product.

⁵ Can be done at Visit 00C or Visit 01A if applicable. The catheter should be removed after the 36-hour time point.

⁶ Hemoglobin, AST, ALT, total bilirubin, BUN, serum creatinine (includes eGFR), serum potassium and magnesium will be checked.

⁷ The study product will be administered orally under direct supervision with a high-fat, high-calorie meal and 240 mL water. A mouth check will be done. Food, liquids, and medication will be restricted for 2 hours post doses. Study participants should eat this meal in 30 ± 10 minutes or less; however, pretomanid should be administered 30 ± 10 minutes after start of the meal.

⁸ Blood can be drawn up to 1 hour prior to dosing.

⁹ The urine PK will be assessed up to 1 hour pre-dose and at 0-4, 4-8, 8-12, 12-24, 24-48, 48-72, and 72-96 hours post-dosing. PK urine sample collection during the 48-72 hours and 72-96 hours may be performed at home (i.e., Day 4 and Day 5).

¹⁰ SAEs only from study drug administration to Day 85 + 7 days.

¹¹ Alcohol testing can be done on blood or breath if breathalyzer is used for alcohol testing.

¹² Participants may remain in the hospital per site decision.

9.7.1 Sample Size

Not Applicable

10.2 Protocol Deviations

Table 3: Distribution of Protocol Deviations by Category, Type, and Impairment Group

[Implementation Note: Only include the Deviation Types that are used for your study. If the table will be multi-page, move the footnote/explanation to the footer so that it repeats for each page of the table.]

Category	Deviation Type	Mild Renal Impairment (N=X)		Moderate Renal Impairment (N=X)		Severe Renal Impairment (N=X)		Matched Controls (N=X)		All Participants (N=X)	
		No. of Ppt.	No. of Dev.	No. of Ppt.	No. of Dev.	No. of Ppt.	No. of Dev.	No. of Ppt.	No. of Dev.	No. of Ppt.	No. of Dev.
Eligibility/enrollment	Any type	x	x	x	x	x	x	x	x	x	x
	Did not meet inclusion criterion	x	x	x	x	x	x	x	x	x	x
	Met exclusion criterion										
	ICF not signed prior to study procedures										
	Other										
Treatment administration schedule	Any type										
	Out of window visit										
	Missed visit/visit not conducted										
	Missed treatment administration										
	Delayed treatment administration										
	Other										
Follow-up visit schedule	Any type										
	Out of window visit										
	Missed visit/visit not conducted										
	Other										
Protocol procedure/assessment	Any type										
	Incorrect version of ICF signed										
	Blood not collected										

Table 3: Distribution of Protocol Deviations by Category, Type, and Impairment Group (continued)

Category	Deviation Type	Mild Renal Impairment (N=X)		Moderate Renal Impairment (N=X)		Severe Renal Impairment (N=X)		Matched Controls (N=X)		All Participants (N=X)	
		No. of Ppt.	No. of Dev.	No. of Ppt.	No. of Dev.	No. of Ppt.	No. of Dev.	No. of Ppt.	No. of Dev.	No. of Ppt.	No. of Dev.
	Urine not collected										
	Stool not collected										
	Other specimen not collected										
	Too few aliquots obtained										
	Specimen result not obtained										
	Required procedure not conducted										
	Required procedure done incorrectly										
	Study product temperature excursion										
	Specimen temperature excursion										
	Other										
Treatment administration	Any type										
	Required procedure done incorrectly										
	Study product temperature excursion										
	Other										
Blinding policy/procedure	Any type										
	Treatment unblinded										
	Other										

12.2.2 Displays of Adverse Events

Please refer to Common Terminology Criteria for Adverse Events (CTCAE) Version 5.0, November 2017:
https://ctep.cancer.gov/protocoldevelopment/electronic_applications/ctc.htm#ctc_50

12.4.1 Individual Laboratory Measurements and Abnormal Laboratory Values

Please refer to Common Terminology Criteria for Adverse Events (CTCAE) Version 5.0, November 2017:

https://ctep.cancer.gov/protocoldevelopment/electronic_applications/ctc.htm#ctc_50

14.1 Description of Study Participants

14.1.1 Disposition of Participants

Table 4: Participant Disposition by Impairment Group

[Implementation Note: The endpoint milestone listed should be the blood draw of your primary endpoint, or whatever milestone(s) is appropriate for your protocol.]

This table may be presented by cohort instead of, or in addition to, treatment arm, as appropriate. If presented by cohort, then cohort-specific screening counts may be included in row 1.

Percentages are calculated using the denominators displayed in the header. These denominators are the numbers of participants who enrolled into the study for each group.]

Participant Disposition	Mild Renal Impairment (N=X)		Moderate Renal Impairment (N=X)		...		All Participants (N=X)	
	n	%	n	%	n	%	n	%
Screened	--	--	--	--	--	--	x	--
Enrolled/Randomized	x	100	x	100	x	xx	x	100
Received Treatment	x	xx	x	xx	x	xx	x	xx
Received All Scheduled Treatments ^a	x	xx	x	xx	x	xx	x	xx
Completed Final Blood Draw [include appropriate endpoint milestones]								
Completed Follow-up (Study Day XXX) ^a								
Completed Per Protocol ^b								

Note: N = All Enrolled Participants.

^a Refer to Listing 16.2.1 for reasons participants discontinued or terminated early.

^b Refer to Listing 16.2.3 for reasons participants are excluded from the Analysis populations.

Table 5: Analysis Populations by Impairment Group

[Implementation Note: The reasons listed here should match the SAP text that describes who will be excluded from analyses. Although participants may meet multiple criteria for exclusion, they should be counted under only one reason for exclusion in this table. Priority for assigning reasons for exclusions will be defined in the SAP text.]

Analysis Populations	Reason Participants Excluded	Mild Renal Impairment (N=X)		Moderate Renal Impairment (N=X)		Severe Renal Impairment (N=X)		Matched Controls (N=X)		All Participants (N=X)	
		n	%	n	%	n	%	n	%	%	n
Safety Population	Any Reason	x	xx	x	xx	x	xx	x	xx	x	xx
	Did not receive study product										
	[Reason 2]										
	[Reason 3]										
	[Reason 4]										
Pharmacokinetic Population	Any Reason										
	[Reason 1]										
	[Reason 2]										
PK Plasma Population	Any Reason										
PK Urine Population	Any Reason										

Table 6: Dates of First Treatment by Site and Impairment Group

[Implementation Note: If the number of sites and/or groups causes this table to be too wide (wider than the page), then break into 2 tables: one by site and one by treatment group, similar to the demographics tables.]

This table is displayed by both Site and Treatment group (for multicenter studies). It is important to look at enrollment over time, especially for a study of a disease with a particular season (e.g., flu), or if there were multiple lots of a product used. Enrollment data over time is displayed by group to confirm that treatments were balanced across time, by site to show if a site enrolled in a different time period than the other sites (in a way that might affect their results.)]

Dates of Dosing	Alliance for Multispecialty Research Mild Renal Impairment (N=X)	Alliance for Multispecialty Research Moderate Renal Impairment (N=X)	...	Advanced Pharma Mild Renal Impairment (N=X)	Advanced Pharma Moderate Renal Impairment (N=X)	...	All Sites Mild Renal Impairment (N=X)	All Sites Moderate Renal Impairment (N=X)	...	All Sites All Participants (N=X)
Total (Entire period of enrollment)										
DDMMYYYY-DDMMYYYY [categorize based on length of enrollment period]	X	X	X	X	X	X	X	X	X	X
Note: N = Number of participants enrolled.										

Table 7: Ineligibility Summary of Screen Failures

Inclusion/Exclusion Category	Inclusion/Exclusion Criterion	n ^a	% ^b
Inclusion and Exclusion	Number of participants failing any eligibility criterion	x	100
Inclusion	Any inclusion criterion	x	xx
	[inclusion criterion 1]	x	xx
	[inclusion criterion 2]	x	xx
	[inclusion criterion 3]	x	xx
Exclusion	Any exclusion criterion	x	xx
	[exclusion criterion 1]	x	xx
	[exclusion criterion 2]	x	xx
	[exclusion criterion 3]	x	xx

^a More than one criterion may be marked per participant.
^b Denominator for percentages is the total number of screen failures.

14.1.2 Demographic Data by Impairment Group

Table 8: Summary of Categorical Demographic and Baseline Characteristics by Site

[Implementation Note: This table may include other categorical baseline characteristics]

Variable	Characteristic	Alliance for Multispecialty Research (N=X)		Advanced Pharma (N=X)		All Participants (N=X)	
		n	%	n	%	n	%
Sex	Male	x	xx	x	xx	x	xx
	Female						
Ethnicity	Not Hispanic or Latino	x	xx	x	xx	x	xx
	Hispanic or Latino						
	Not Reported						
Race	Unknown						
	American Indian or Alaska Native	x	xx	x	xx	x	xx
	Asian						
	Native Hawaiian or Other Pacific Islander						
	Black or African American						
	White						
	Multi-Racial						
	Unknown						

Note: N = Number of participants enrolled.

Table 9: Summary of Continuous Demographic and Baseline Characteristics by Site

[Implementation Note: For studies in infants or young children, may be more appropriate to summarize age by months or weeks. This table may include additional continuous baseline characteristics (e.g., height, weight, BMI).]

Variable	Statistic	Alliance for Multispecialty Research (N=X)	Advanced Pharma (N=X)	All Participants (N=X)
Age (years)	Mean	xx	xx	xx
	Standard Deviation	xx	xx	xx
	Median	xx	xx	xx
	Minimum	x	x	x
	Maximum	x	x	x
Height (cm)	Mean	xx	xx	xx
	Standard Deviation	xx	xx	xx
	Median	xx	xx	xx
	Minimum	x	x	x
	Maximum	x	x	x
Weight (kg)	Mean	xx	xx	xx
	Standard Deviation	xx	xx	xx
	Median	xx	xx	xx
	Minimum	x	x	x
	Maximum	x	x	x
BMI (kg/m ²)	Mean	xx	xx	xx
	Standard Deviation	xx	xx	xx
	Median	xx	xx	xx
	Minimum	x	x	x
	Maximum	x	x	x

Note: N = Number of participants enrolled.

Table 10: Summary of Categorical Demographic and Baseline Characteristics by Impairment Group, All Enrolled Participants

[Implementation Note: This table may include other categorical baseline characteristics and may be generated for multiple analysis populations in addition to all enrolled participants. The N's should match the number of participants in the analysis population.]

Variable	Characteristic	Mild Renal Impairment (N=X)		Moderate Renal Impairment (N=X)		...		All Participants (N=X)	
		n	%	n	%	n	%	n	%
Sex	Male	x	xx	x	xx	x	xx	x	xx
	Female								
Ethnicity	Not Hispanic or Latino	x	xx	x	xx	x	xx	x	xx
	Hispanic or Latino								
	Not Reported								
	Unknown								
Race	American Indian or Alaska Native	x	xx	x	xx	x	xx	x	xx
	Asian								
	Native Hawaiian or Other Pacific Islander								
	Black or African American								
	White								
	Multi-Racial								
	Unknown								

Note: N = Number of enrolled participants.

Table 11: Summary of Continuous Demographic and Baseline Characteristics by Impairment Group, All Enrolled Participants

[Implementation Note: For studies in infants or young children, may be more appropriate to summarize age by months or weeks. This table may include other continuous baseline characteristics.]

Variable	Statistic	Mild Renal Impairment (N=X)	Moderate Renal Impairment (N=X)	...	All Participants (N=X)
Age (years)	Mean	xx	xx	xx	xx
	Standard Deviation	xx	xx	xx	xx
	Median	x	x	x	x
	Minimum	x	x	x	x
	Maximum	x	x	x	x
Height (cm)	Mean	xx	xx	xx	xx
	Standard Deviation	xx	xx	xx	xx
	Median	xx	xx	xx	xx
	Minimum	x	x	x	x
	Maximum	x	x	x	x
Weight (kg)	Mean	xx	xx	xx	xx
	Standard Deviation	xx	xx	xx	xx
	Median	xx	xx	xx	xx
	Minimum	x	x	x	x
	Maximum	x	x	x	x
BMI (kg/m ²)	Mean	xx	xx	xx	xx
	Standard Deviation	xx	xx	xx	xx
	Median	xx	xx	xx	xx
	Minimum	x	x	x	x
	Maximum	x	x	x	x
Note: N = Number of enrolled participants.					

14.1.3 Prior and Concurrent Medical Conditions**Table 12: Summary of Participants with Pre-Existing Medical Conditions by MedDRA System Organ Class and Impairment Group**

MedDRA System Organ Class	Mild Renal Impairment (N=X)		Moderate Renal Impairment (N=X)		...		All Participants (N=X)	
	n	%	n	%	n	%	n	%
Any SOC	x	xx	x	xx	x	xx	x	xx
[SOC 1]								
[SOC 2]								

Note: N = Number of participants enrolled. n = Number of participants reporting medical history within the specified SOC. A participant is only counted once per SOC.

Table 13: Summary of Participants with Pre-Existing Medical Conditions by MedDRA Preferred Term and Impairment Group

MedDRA Preferred Term	Mild Renal Impairment (N=X)		Moderate Renal Impairment (N=X)		...		All Participants (N=X)	
	n	%	n	%	n	%	n	%
Any PT	x	xx	x	xx	x	xx	x	xx
[PT 1]								
[PT 2]								

Note: N = Number of participants enrolled. n = Number of participants reporting medical history within the specified PT. A participant is only counted once per PT.

Table 14: Summary of Participants with Newly Developed Medical Conditions by MedDRA System Organ Class and Impairment Group

MedDRA System Organ Class	Mild Renal Impairment (N=X)		Moderate Renal Impairment (N=X)		...		All Participants (N=X)	
	n	%	n	%	n	%	n	%
Any SOC	x	xx	x	xx	x	xx	x	xx
[SOC 1]								
[SOC 2]								

Note: N = Number of participants enrolled. n = Number of participants reporting medical history within the specified SOC. A participant is only counted once per SOC.

Table 15: Summary of Participants with Newly Developed Medical Conditions by MedDRA Preferred Term and Impairment Group

MedDRA Preferred Term	Mild Renal Impairment (N=X)		Moderate Renal Impairment (N=X)		...		All Participants (N=X)	
	n	%	n	%	n	%	n	%
Any PT	x	xx	x	xx	x	xx	x	xx
[PT 1]								
[PT 2]								

Note: N = Number of participants enrolled. n = Number of participants reporting medical history within the specified PT. A participant is only counted once per PT.

14.3 Safety Data

14.3.1 Displays of Adverse Events

Table 16: Overall Summary of Adverse Events

	Mild Renal Impairment (N = x)		Moderate Renal Impairment (N = x)		...		All Participants (N = x)	
	n	%	n	%	n	%	n	%
Participants ^a with								
At least one lab finding of mild or worse severity through Day 12	x	x	x	x	x	x	x	x
At least one unsolicited adverse event	x	x	x	x	x	x	x	x
At least one unsolicited treatment emergent adverse event	x	x	x	x	x	x	x	x
At least one related unsolicited treatment emergent adverse event	x	x	x	x	x	x	x	x
Mild (Grade 1)	x	x	x	x	x	x	x	x
Moderate (Grade 2)	x	x	x	x	x	x	x	x
Severe (Grade 3)	x	x	x	x	x	x	x	x
Not yet assessed								
At least one severe (Grade 3) unsolicited treatment emergent adverse event	x	x	x	x	x	x	x	x
Related	x	x	x	x	x	x	x	x
Unrelated	x	x	x	x	x	x	x	x
At least one treatment emergent serious adverse event ^b	x	x	x	x	x	x	x	x
At least one related treatment emergent serious adverse event	x	x	x	x	x	x	x	x
At least one treatment emergent adverse event leading to early termination ^c	x	x	x	x	x	x	x	x

N = Number of participants in the Safety Population

^a Participants are counted once for each category regardless of the number of events.

^b A listing of Serious Adverse Events is included in the Listing of Serious Adverse Events table.

^c As reported on the Adverse Event eCRF.

Table 17: Treatment Emergent Adverse Events Occurring in 5% of Participants in Any Impairment Group by MedDRA System Organ Class and Preferred Term, and Impairment Group - Safety Population

[Implementation Note: this table is used to complete the “Other Adverse Event Template” for clinicaltrials.gov reporting (See slide 6 in <https://prsinfo.clinicaltrials.gov/trainTrainer/Adverse-Events-Module.pdf>). Threshold value may be 0% to 5% (default 5). This table should include a row for All PT/SOC and for any PT/SOC reported by \geq [threshold] % participants in any group. Note, this table summarize SAEs and non-serious events separately. This includes all adverse events collected (e.g., solicited, unsolicited, AESI, laboratory adverse events, etc.), regardless of relationship to study product, so this summary should combine data collected across multiple eCRFs/domains.]

Preferred Term	MedDRA System Organ Class	Mild Renal Impairment (N=X)			Moderate Renal Impairment (N=X)			...			All Participants (N=X)		
		n	%	Events	n	%	Events	n	%	Events	n	%	Events
Serious Adverse Events													
All	All	x	x	x	x	x	x	x	x	x	x	x	x
PT1	SOC1	x	x	x	x	x	x	x	x	x	x	x	x
Etc.	Etc.												
Other (Non-serious) Adverse Events													
All	All	x	x	x	x	x	x	x	x	x	x	x	x
PT1	SOC1	x	x	x	x	x	x	x	x	x	x	x	x
Etc.	Etc.												

N = number of participants in the Safety Population (number of participants at risk).
n= number of participants reporting event.
Events= total frequency of events reported.

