8.6 Halting Rules

8.6.1 Study Halting Criteria

The study will be immediately suspended, and no additional doses administered if any of the following occurs:

- Any death occurring during the study that was not the result of trauma or accident.
- Two or more participants experience an SAE, related to the study product.
- Three or more participants in each part of the trial (A or B) develop a severe, Grade 3 or higher, AE, systemic or laboratory, in the same MedDRA Low Level Term (LLT), assessed as related to the study product.

If any halting criterion is met, the study will be suspended, and a SMC *ad hoc* meeting will convene. The study will not be re-started until the SMC meets and provides its recommendation to DMID, the study sponsor.

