10.5.3.1 Adverse Events

AEs will be coded using Medical Dictionary for Regulatory Activities® (MedDRA). All AEs that occur after the receipt of study product will be summarized using the number of events as well as the number and percent of participants experiencing the event. Summaries will be presented by renally impaired and non-renally impaired groups and MedDRA level hierarchy (system organ class [SOC] and preferred term) as follows:

- Overall (i.e., regardless of severity or relationship to treatment)

- By severity grade (mild, moderate, severe, or life-threatening)
- By relationship to study product

Unless otherwise specified, at each level of participant summarization in reporting incidence of AEs, a participant will be counted only once even if the participant reported one or more events. If more than one occurrence of an event is reported, the event of the worst severity or the worst-case relationship assessment will be summarized.

The number of SAEs is expected to be small, as such these events will be reported in detailed listings showing the event description, MedDRA preferred term and SOC, event date, severity, relatedness, and outcome for each event.

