9.3 Adverse Events

An AE is defined as any untoward medical occurrence in a clinical study participant administered a medicinal product, which does not necessarily have a causal relationship with this treatment. An AE can therefore be any unfavorable or unintended sign (including an abnormal laboratory finding), symptom, or disease temporally associated with the use of a medicinal (investigational) product, whether or not it is related to the medicinal (investigational) product. This includes exacerbation of a pre-existing condition or events, intercurrent illnesses, drug interaction or the significant worsening of the indication under investigation that is not recorded elsewhere in the eCRF under specific efficacy assessments. Anticipated fluctuations of pre-existing conditions, including the condition under study, that do not represent a clinically significant exacerbation or worsening need not be considered AEs.

It is the responsibility of the Investigator to document all AEs that occur during the study. AEs must be reported on the appropriate page(s) of the eCRF. All AEs will be coded using the MedDRA dictionary Version 27.0 or higher.

TEAEs are defined as any event that occurs or worsens on or after the day that study treatment initiated. AEs recorded in the eCRF which began prior to treatment will not be included in the summary tables but will be included in the AE data listings ([Listing 9](#)).

The severity of AEs will be graded according to National Cancer Institute (NCI) Common Terminology Criteria for Adverse Events (CTCAE) Version 5.0. The severity of the AE should be the maximum over the course of the AE. For AEs not listed in the NCI CTCAE, the Investigator should determine the severity of the AE according to the following criteria, as described in Section 8.1.1.1 of the protocol.

- Mild (Grade 1): Asymptomatic or mild symptoms, Events require minimal or no treatment and do not interfere with the participant's daily activities.
- Moderate (Grade 2): Events result in a low level of inconvenience or concern with therapeutic measures. Moderate events may cause some interference with functioning and daily activities.
- Severe (Grade 3): Severe or medically significant but not immediately life threatening, interrupt the participant's daily activities; and may require intervention and hospitalization. Severe events are usually incapacitating.
- Life-threatening (Grade 4): Life-threatening consequences; urgent intervention indicated.

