9.3.2 Unsolicited Adverse Events

An overall summary of AEs will be presented ([Table 19](#)) that includes the number of events and the number and percentage of participants who experienced at least one AE or TEAE, by renal impairment group. This summary will also include treatment-related TEAEs, SAEs, and TEAEs leading to early termination. AEs will be summarized using discrete summary statistics and presented at the participant level. TEAEs will also be summarized ([Table 21](#) through [Table 24](#)) by renal impairment group in a separate table at the event level by MedDRA SOC and PT. If a participant reports the same PT multiple times within the same SOC, that PT will only be reported once within that SOC. As with the PT, if a participant reports multiple conditions within the same SOC, that SOC will only be reported once at the SOC summary level. SOCs will be reported in ascending alphabetical order, PTs will be listed in order of descending frequency for all participants included in the table within each SOC.

TEAEs that occur in 5% of participants in any impairment group will be presented ([Table 20](#)) by SOC, PT and impairment group.

A summary of TEAEs by maximum severity will be presented ([Table 25](#)). The number of participants within any TEAEs (along with percentages) will be tabulated by SOC and PT within each SOC by renal impairment group. To count the number of participants within any TEAEs, if a participant has multiple TEAEs coded to the same PT within the same SOC, the participant will be counted once under that maximum severity.

Summaries of related TEAEs will be presented ([Table 26](#) through [Table 29](#)) by impairment group, SOC, and PT.

The denominator for all percentages will be the number of participants being summarized.

A bar chart of serious and non-serious related TEAEs by SOC will also be presented ([Figure 2](#) and [Figure 3](#))

All AEs will be listed ([Listing 9](#)). All SAEs will also be listed separately ([Table 30](#)). Non-serious, moderate or severe adverse events will be listed ([Table 31](#)). Other significant adverse events will also be listed ([Table 32](#)).

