14.3.2 Listing of Deaths, Other Serious and Significant Treatment Emergent Adverse Events

Table 27: Listing of Serious Adverse Events

[Implementation Note: This listing is included in the table shells document, as it is included in the body of the CSR. If the event is ongoing (no stop date), indicate “ongoing” for the “Duration”. If more than one reason is selected for the reason reported as an SAE, list all reasons in the column, separated by a comma. In the “If Not Related, Alternate Etiology” column, merge the 2 data fields for collecting alternate etiology, separate by a colon. If there are no comments for an event, populate ‘Comments’ row with ‘None’. Add columns for MedDRA HLT or LLT depending on halting criteria or other study needs. In the CSR, Participant ID should be USUBJID (not PATID) for purposes of de-identification. Listing should be sorted by Participant ID, Associated with Dose No., and No. of Days Post Associated Dose.]

Adverse Event	No. of Days Post Dose (Duration)	No. of Days Post Dose the Event Became Serious	Reason Reported as an SAE	Severity	Relationship to Study Treatment	If Not Related, Alternative Etiology	Participant Discontinued Due to AE	Outcome	MedDRA System Organ Class	MedDRA Preferred Term
Participant ID: Impairment Group: , AE Number:										
Comments:										
Participant ID: Impairment Group: , AE Number:										
Comments:										

Table 28: Listing of Non-Serious, Unsolicited, Moderate or Severe Adverse Events

[Implementation Note: This listing is included in the tables document, as it is included in the body of the CSR. If the event is ongoing (no stop date), indicate “ongoing” in the “Duration” column. In the “If Not Related, Alternate Etiology” column, merge the 2 data fields for collecting alternate etiology, separate by a colon. If there are no comments for an event, populate ‘Comments’ row with ‘None’. Add columns for MedDRA HLT or LLT depending on halting criteria or other study needs. In the CSR, Participant ID should be USUBJID (not PATID) for purposes of de-identification. Listing should be sorted by Participant ID, Associated with Dose No., and No. of Days Post Associated Dose.]

Adverse Event	No. of Days Post Dose (Duration)	Severity	Relationship to Study Treatment	If Not Related, Alternative Etiology	Participant Discontinued Due to AE	Outcome	MedDRA System Organ Class	MedDRA Preferred Term
Participant ID: Impairment Group: , AE Number:								
Comments:								

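### SAP Table 16 has no Grade 4 category and its severe row counts Grade 3 only, and the non-serious AE listing names only moderate and severe events (minor)

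*SAP*

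**What the plan says.** Table numbers here are those of the SAP Appendix 1 shells. The text of SAP 9.3.2 cites the same outputs under other numbers: Table 19 for the overall summary, 25 for maximum severity, 30 for SAEs and 31 for the non-serious listing.

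- **Scale.** Protocol 8.1.1.1 and SAP 9.3 define the same four grades. The last is "Life-threatening (Grade 4): Life-threatening consequences; urgent intervention indicated". SAP 9.3 records an event's severity as the maximum reached over its course.
- **Protocol commitment.** Protocol 10.5.3.1 promises AE summaries "By severity grade (mild, moderate, severe, or life-threatening", with repeated occurrences of an event summarised at the worst severity.
- **Table 16.** The parent row for related treatment-emergent events has sub-rows for Grade 1, Grade 2, "Severe (Grade 3") and not yet assessed. The next row is "At least one severe (Grade 3) unsolicited treatment emergent adverse event", split into related and unrelated. A separate row, "At least one treatment emergent serious adverse event", counts serious events without grade.
- **Listing.** SAP 9.3.2 says "Non-serious, moderate or severe adverse events will be listed". The shell, Table 28, is titled "Listing of Non-Serious, Unsolicited, Moderate or Severe Adverse Events".
- **Table 22.** This maximum-severity table carries a life-threatening row, by relationship and impairment group.

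**The concern.** Table 16 is the summary most readers of the study report will look at first, and it has no place for the highest grade on the study's own scale. Because severity is recorded as the maximum over the event, one AE that worsens from Grade 3 to Grade 4 is stored as Grade 4 and leaves the severe row. A worse outcome can thus lower the severe count. A group with one Grade 4 event could appear to have fewer severe events than a group with one Grade 3 event.

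The listing has a similar gap. It would show a non-serious Grade 2 event but, on its wording, not a non-serious Grade 4 event.

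**Working it through.** The documents give no figure to reproduce. The check compares each AE output with the four-grade scale and then works through one example.

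**Step 1. Grades covered by each output**

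| Output | Grade 4 shown? |
|---|---|
| Table 16, related sub-rows | No (Grades 1, 2, 3) |
| Table 16, severe row | No (Grade 3 only) |
| SAP 9.3.2 text and Table 28 | Not named (Grades 2 and 3) |
| Table 22, maximum severity | Yes, by relationship and group |
| Laboratory severity and shift tables | Yes |
| Listing 9, all unsolicited AEs | Yes, severity column |
| Table 27, SAEs | Yes if serious, severity column |

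Table 16 covers 3 of 4 grades and Table 22 covers 4 of 4. The SAP gives no reason for the difference.

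**Step 2. Who is missed in Table 16**

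- If the sub-rows count each participant at worst grade, anyone whose worst related event is Grade 4 is in the parent row and in no graded sub-row.
- If they count any event of the named grade, the gap affects those with no related event of a lower grade.
- The severe row omits a participant whose only Grade 3-or-higher event is Grade 4.

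**Step 3. Example (assumed data)**

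Three participants each have one related event, two at Grade 3 and one at Grade 4.

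- Table 16 parent row: 3.
- Table 16 sub-rows: 0 + 0 + 2 + 0 = 2, which does not account for the parent row.
- Table 16 severe row: 2.
- Table 22, any organ class and any term, related: severe 2 + life-threatening 1 = 3.
- Table 16 after the fix: the Grade 3-or-higher row is 2 + 1 = 3, which agrees with Table 22.

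**Step 4. Size of one missed participant**

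- A group of 6: 1/6 = 16.7 percentage points.
- Pooled matched controls if Part B runs, up to 18: 1/18 = 5.6 points.
- SAP section 17 displays the severe arm as two columns, severe and ESRD not on dialysis. If the 6 split 3 and 3 (an assumption): 1/3 = 33.3 points.

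**Step 5. Can a Grade 4 event be non-serious?**

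Protocol 8.1.2 makes a life-threatening AE serious and defines that as immediate risk of death. Protocol 8.5 grades laboratory results by CTCAE, which is a separate judgement from seriousness. A non-serious Grade 4 laboratory AE is therefore not ruled out. It would fall outside Table 27 and outside the wording of Table 28.

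**The case against.** The strongest reply is that nothing is lost from the planned analysis. Table 22 already delivers the four-grade summary promised in Protocol 10.5.3.1, and Grade 3 or higher can be read from it by adding two rows. That stands. A reader might infer from Table 16 that the worst events disappear from the SAP's severity counts. The documents do not support that, given Table 22, the laboratory tables and Listing 9.

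The listing gap is also narrow. A clinically life-threatening AE is serious by definition and goes to Table 27. The gap needs a Grade 4 laboratory AE judged non-serious, and the documents do not reproduce the CTCAE thresholds, so its likelihood cannot be estimated from them. Even then Listing 9 and the abnormal laboratory listings (Tables 30 and 31) would show it. The Grade 4 laboratory columns are not a forecast of such events: they look like generic template columns, since the creatinine shell even has a low Grade 4 column.

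A reader might also infer that Table 16 undermines the halting rule, because Protocol 8.6.1 counts participants who "develop a severe, Grade 3 or higher, AE, systemic or laboratory". That does not follow. The rule requires three or more participants, within one study part, in the same MedDRA Low Level Term, with related events. Table 16 shows neither part nor term, so it could not serve as a halting display even after correction. Halting is applied during the study through the Medical Monitor and the Safety Monitoring Committee, while SAP section 1 describes the shells as planned for the final analyses.

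Finally, SAP section 1 allows minor changes to table design. That makes the fix easy, but the shell as written is still out of step with Table 22 and with the grading scale.

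**Conclusion.** The point holds as a minor error in one summary table and one listing. As written, Table 16 leaves the worst grade out of its severity counts, its sub-rows can fail to account for the parent row, and it can disagree with Table 22. The wording of SAP 9.3.2 and Table 28 leaves out a non-serious Grade 4 event.

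The effect is one participant at a time, with the percentages shown above. It arises only if a Grade 4 event occurs, and for the severe row only if that participant has no Grade 3 event as well. The documents give no expected frequency. No PK estimate, analysis population or halting decision changes.

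**What to change.** - **Table 16:** add a *Life-threatening (Grade 4)* sub-row under related treatment-emergent events. Change the severe row to *At least one Grade 3 or higher unsolicited TEAE*, keeping the related and unrelated split.
- **Table 28 and SAP 9.3.2:** change the scope to *non-serious, Grade 2 or higher*.

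The cost is two shell edits and one sentence of SAP text. No new data, analysis or protocol amendment is needed. It is best done before the tables are programmed.
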